5.3 Per-Protocol Population

A second per-protocol (PP) data set will be defined excluding any subjects with major deviations or lack of compliance with taking their assigned study treatment. The PP dataset will be used only for the primary efficacy analysis (3M oral rinse vs. vehicle control) and the secondary efficacy analysis with all four treatment groups.

The following major protocol deviations will lead to exclusion from the per protocol data set:

- (1) Subject who is missing either one or both primary endpoints of GI and PI values at 6 months
- (2) Subject who did not meet the inclusion criteria of baseline Gingival Index (GI) score of ≥ 1.0 and a baseline Plaque index (PI) score of ≥ 1.5 .
- (3) Subject with $< 80\%$ of planned dose (or alternatively $>20\%$ of no rinsing).
- (4) Subject with ≥ 3 consecutive days of no rinsing within 4 weeks prior to PI and GI assessments.
- (5) Subject who indicated antibiotics, anti-inflammatory, anticoagulants, or immunosuppressant drug use, regardless of dose, within 6 weeks prior to PI and GI assessments.

All deviations not captured above that will result in exclusion from the PP analysis will be defined and justified in a blinded fashion. In addition, documentation will be made of these data classification decisions prior to data lock.

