6.3 SAS Imputation Procedures

SAS PROC MI procedure will be used to perform imputations of the missing primary variables, namely, the PI and GI indices. The EM algorithm assumes multivariate normal distribution for the data; PI and GI values (baseline values included). The missing data for a given treatment group will be imputed independently with input data being the PI and GI data at all time points (baseline, 3 months and 6 months) from only that treatment group. The imputation procedure is valid when the missing data are missing at random. %MULTINORM macro can test for multivariate normality and PROC MI can display patterns of missing data.

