Blinding:	
The Principal Investigator and clinical examiners will be blinded to the treatment products. No clinical examiners will see the allocated rinse assigned per the randomization schedule. Due to the rinse packaging differences and to maintain the blind, all study products will be placed in a non-transparent container. Subjects will be told not to open the container until they return to their home and to bring study supplies back to their next scheduled appointment in the same container. Only the study coordinator at the site will know the randomization assignment.

Outcome Measures:	
 • Modified Quigley-Hein Plaque Index at baseline, 3 and 6 months (\pm 10 days) • Löe-Silness Gingival Index at baseline, 3 and 6 months (\pm 10 days) • Eastman Interdental Bleeding Index at baseline, 3 and 6 months (\pm 10 days) • Oral soft and hard tissue assessment baseline, 3 and 6 months (\pm 10 days) • Adverse Events
Study Restrictions	
Subjects will only use the study toothpaste, toothbrush, dental floss and mouth rinses that are provided by the study staff and will refrain from using any other oral hygiene products or measures such as other toothpaste, mouth rinse, mechanical toothbrush and chewing gum etc.
 
Subjects will not eat or drink 4 hours before clinical exams, and will not brush or floss their teeth the night before and the morning of the clinical exams.

Clinical Safety Assessment	
Safety assessments will be completed by a clinical examiner at each clinical visit.

Data Analysis Plan:	
Means and standard deviations will be calculated for all clinical measurements and assessments. Categorical variables will be summarized in frequency distributions. Analysis of variance (ANOVA) or (ANCOVA) will be used to test for treatment group differences between the subject groups at 3 and 6 months.
 
GI, PI, and BI scores will be calculated as the average tooth score across all teeth as one score per patient, per visit.
 
All statistical analyses will be performed using SAS version 9.3 or above (SAS Institute, Cary, NC) or another statistical software package.

----------------------------	--

Study Schedule						
	Screening followed by at least a 7-day washout	Baseline	Interim Visits (Approximately) 1.5 and 4.5 months	3-Month (\pm 10 days)	6-Month (\pm 10 days) or upon subject discontinued	Unscheduled visit can occur at any time for any reason

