4.4 Risk/Benefit Summary

4.4.1 Risks and Benefits of the Experimental Device and Clinical Investigation

The anticipated clinical benefit of the 3M Oral Rinse and the predicate oral rinse is control of plaque and gingivitis. Subjects who receive placebos may not receive the same benefit as those who receive active treatment.

Subjects will be instructed to refrain from any dental treatment, including dental prophylaxis, during the study. If necessary, emergency dental treatment may be performed. Subjects will be instructed to inform the investigator as soon as possible if any emergency dental treatment is performed. The investigator will then decide whether the subject should continue in the study. Subjects who receive medical and/or dental treatment with antibiotic management may be dropped from the study.

The following is a list of potential risks associated with this study.

- Plaque and gingivitis may not improve
- Subjects may have an increased risk of disease or infection from altered oral mucosal immunity due to potential changes in oral flora
- Potential allergies to product components
- Oral rinses can cause transient mouth/tongue numbness
- Oral rinses can cause mucosal sloughing/irritation
- Oral rinses can cause transient dry mouth
- Oral rinses may cause transient alteration in taste
- Subjects may experience bleeding gums during study visits with clinicians due to probing/gingivitis assessment procedures
- Subjects should avoid rinse contact with skin and eyes. In case of contact with skin, wash thoroughly and in case of contact with eyes, flush with water.

5. Study Design and Study Objectives/Endpoints

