5.1 Study Design

This is a prospective, single site, randomized, parallel, blinded clinical trial. Subjects will be randomly assigned to one of four treatment groups identified as Product A, Product B, Product C or Product D.

Subjects will be screened for eligibility and entered into a washout period that is at least 7 days, during which time they will be provided with study toothbrush, toothpaste and dental floss. No oral rinses or medication that alters oral tissue health will be used or taken during the washout period. After randomization, the designated rinse will be placed into a non-transparent container so that other subjects and clinical examiners do not see the allocated rinse per the randomization schedule.

Subjects will be provided with both verbal and written instructions to take home, and a diary for tracking dosing compliance and any side effects from rinse use. Subjects will return the diary along with the empty/used/unused rinse bottles in the original container at their next scheduled visit to monitor for compliance of product use. Subjects that are found to be non-compliant will remain in the study, be re-trained and documented accordingly.

Examinations for the clinical endpoints (PI, GI and BI) will be conducted at the baseline, 3-month (± 10 days), and 6-month (± 10 days) visits.

Interim visits will be scheduled to review diary, replenish study supplies, check study compliance, etc. Subjects will be provided Colgate Regular toothpaste, dental floss and a soft toothbrush (replaced at 3 months) for use during the 6-month study period.

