6.6 Withdrawal or Termination of Subjects

A genuine effort will be made to collect all outcome data and keep subjects enrolled in the study. Effort will be made to determine the reason(s) why a subject fails to return to the study site for the necessary visit(s) or has dropped from the study. A subject may withdraw from the study at any time.

A subject may be dropped from the study if any of the following occur:

- Subject fails to show up at the scheduled visits (three attempts will be made to schedule subjects and if they have not responded they will be dropped)
- Subject elects to terminate participation in the study
- Investigator or Study Coordinator elects to withdraw the subject (with written justifications about safety, noncompliance or any other reason)
- Subject experiences a severe adverse reaction to the test product(s)
- Subject begins long-term (12 days or more) treatment with antibiotics
- Subject needs dental therapy that cannot wait until the end of the study
- Subject becomes pregnant

Subjects discontinued from the study for any reason will not be allowed to reenter the study. Subjects withdrawn due to adverse events (AEs) will receive follow-up until the AE is resolved, or is determined by the Investigator to be stable. Final assessments will be completed if possible.

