6.7 Blinding and Randomization

6.7.1 Blinding

The Principal Investigator and clinical examiners will be blinded to the treatment product assigned to study subjects. Efforts will be made to ensure that subject blinding is effective as

possible including precautionary measures such as subjects will be told not to open the non-transparent container containing study products until they return to their home and to bring all study supplies back to their next scheduled appointment in the same container. A subject blinding assessment will be completed after the first rinse dose and at the last study visit.

The blind will not be broken during the study unless 3M personnel decide to stop the study or it is necessary to break the blind for subject safety.

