9.2 Unscheduled Visits

An unscheduled visit can occur any time during the study if the investigator believes the subject should be evaluated. The subjects will be instructed to notify the Study Coordinator or Principal Investigator with any medical/dental issues (cannot tolerate the rinse, oral issues, adverse events etc.) If the subject is requested to return to the clinic for an assessment/examination, this visit will be collected on the “unscheduled visit” form.

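### Protocol 6.6 lets the study coordinator, the only site role that knows the assignment, withdraw a subject without the blinded investigator's agreement; a cheap, minor wording change would close this

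*Combined protocol and SAP*

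**What the plan says.** Protocol 6.6 gives a list of reasons for which a subject may be dropped. One is discretionary: "Investigator or Study Coordinator elects to withdraw the subject (with written justifications about safety, noncompliance or any other reason". A written reason is needed, but either role may act alone, and the reason is open-ended. The same section bars discontinued subjects from re-entering, and protocol 11.8 says dropouts are not replaced.

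On blinding, protocol 6.7.1 states: "The Principal Investigator and clinical examiners will be blinded to the treatment product assigned to study subjects". The synopsis adds, and SAP 3.3 repeats: "Only the study coordinator at the site will know the randomization assignment".

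In one related situation, emergency dental treatment, protocol 4.4.1 names a single decision-maker: "The investigator will then decide whether the subject should continue in the study".

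On noncompliance, protocol 5.1 sets the usual course: "Subjects that are found to be non-compliant will remain in the study, be re-trained and documented accordingly". SAP 5.3 deals with it in the analysis through a per-protocol set, "excluding any subjects with major deviations or lack of compliance with taking their assigned study treatment".

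On tolerability, protocol 9.2 tells subjects to "notify the Study Coordinator or Principal Investigator with any medical/dental issues (cannot tolerate the rinse, oral issues, adverse events etc".

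On missing scores, SAP 6.3 states: "The missing data for a given treatment group will be imputed independently with input data being the PI and GI data". The method is the EM algorithm under missing at random. SAP 6.2 adds last observation carried forward and group means as sensitivity analyses.

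**The concern.** PI and GI are scored by an examiner, so the trial depends on keeping knowledge of the assignment away from decisions that shape the 6-month data. Whether a subject stays to be scored is such a decision. Section 6.6 lets the one unblinded site role take it alone.

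If withdrawals were influenced by the assignment, subjects expected to do badly could be lost more often from one arm than from the other. Imputation within arm would repair part of this but not all. Withdrawal that depends only on the arm, or on PI and GI values already recorded, fits the planned model. Withdrawal prompted by something outside the model, such as a complaint about tolerating the rinse, does not. Under protocol 9.2 such complaints may reach either the coordinator or the Principal Investigator.

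**Working it through.** **1. The plan's own figure.** Protocol 11.8 gives 34 per group for 90% power: difference 0.40, SD 0.5, one-sided alpha 0.025. The normal approximation gives 2 × (1.960 + 1.282)² / (0.40/0.5)² = 32.8, so 33. The two-sample t-test gives 33.8, so 34, with power 0.902. The figure reproduces. At the 50 per group to be recruited, power is 0.977, and 1 − 34/50 = 32% can be lost before falling to 34. Power is therefore not at stake; only bias is.

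**2. Who decides and who knows.**

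| Role | May withdraw at discretion (6.6) | Knows the assignment |
|---|---|---|
| Investigator | Yes, alone | No (6.7.1) |
| Study coordinator | Yes, alone | Yes (synopsis; SAP 3.3) |

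No section requires the first role to agree with the second.

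**3. What knowing the assignment means.** Protocol 5.1 and 7.7 identify products by the letters A to D. The SAP 3.1 table links A to the 3M Oral Rinse, and the synopsis says that packaging differs between rinses. The 10 mL label marks PerioShield, but that arm is outside the primary comparison. The test rinse and the vehicle are both dosed at 15 mL. No section says whether the site holds the key to the letters. That the coordinator can tell test rinse from vehicle is thus a plausible inference, not a stated fact.

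**4. Size, by illustration.** From the documents: n = 50 per arm, SD 0.5, within-arm EM on PI and GI at baseline, 3 and 6 months. Assumed: equal between-visit correlation r of 0.3 to 0.7 within an index; same-visit PI–GI correlation c of 0.2 to 0.5, and c × r across index and visit; outside information correlated q = 0.2 to 0.5 with the part of 6-month GI that earlier scores do not predict. Also assumed: the k subjects worst on that information, all in one arm, lose both 6-month scores.

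- Residual SD of 6-month GI = 0.5 × √(1 − 2r²/(1 + r)) = 0.464, 0.408 and 0.325 for r = 0.3, 0.5 and 0.7.
- Shift of the arm mean = q × residual SD × m × k/(50 − k), where m is the mean of the top k of 50 normal order statistics: 2.249 for k = 1 and (2.249 + 1.855)/2 = 2.052 for k = 2.
- One withdrawal: from 0.2 × 0.325 × 2.249/49 = 0.0030 to 0.5 × 0.464 × 2.249/49 = 0.0106.
- Two withdrawals: from 0.2 × 0.325 × 2.052 × 2/48 = 0.0056 to 0.5 × 0.464 × 2.052 × 2/48 = 0.0198.
- PI moves by c times the GI shift: about 0.001 to 0.005 for one and 0.001 to 0.010 for two.

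A simulation of the same set-up (8,000 replicates per cell) gave GI shifts of 0.0030 to 0.0107 for one and 0.0055 to 0.0196 for two.

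**5. Scale.** Against the planned 0.40, the GI shift is about 1% to 3% for one and 1% to 5% for two. The ANCOVA standard error is 0.5 × √(2/50) × √(1 − r²) = 0.095 (r = 0.3) to 0.071 (r = 0.7). The largest shift, 0.0198/0.095, is about 0.2 standard errors. Taken alone, one-sided error on GI would go from 0.025 to about 0.030 to 0.040 with two such withdrawals from the test arm. Success needs both PI and GI, so the effect on the trial's conclusion is smaller. Equal selection in both arms cancels.

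**The case against.** The best case for leaving 6.6 alone is that the plan already has many controls: a written justification and an effort to keep subjects (6.6), examinations scheduled on discontinuation (synopsis), an ITT set of all randomized subjects (SAP 5.2), monitor verification (protocol 10), investigator signature of each eCRF (13.1), discontinuation reasons by arm (SAP 7.1), and sensitivity analyses. These make misuse visible and limit the harm. What remains is that none puts a blinded decision before a step that cannot be undone. An early exit examination also does not replace a 6-month score, and the plan does not say how it would enter the analysis.

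The illustration is also close to a worst case, since it picks exactly the worst subjects, all from one arm, with complete loss of their scores. That is fair, and it supports rating the point low.

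Four stronger readings are tempting, and the documents do not support them:

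- *That 5.1 and 6.6 contradict each other on noncompliance.* Section 6.6 is permissive. Retaining and re-training is the default, and withdrawal is a documented exception. Deleting noncompliance from 6.6 would achieve little, because the open-ended ground would remain.
- *That the coordinator is known to distinguish test rinse from vehicle.* That is inference, as set out in the working.
- *That withdrawal depending on the arm is enough to bias the result.* Imputation is done within each arm, so dependence on arm alone causes no bias.
- *That 4.4.1 shows all such decisions were meant for the investigator.* It covers one clinical situation. It shows only that the arrangement is workable.

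**Conclusion.** The point holds as a minor design improvement. The protocol lets the only unblinded site role end a subject's participation at discretion, without a blinded decision. This opens an avoidable route to loss of 6-month scores influenced by the assignment. It does not show that the route was used or is expected to be, and it is no challenge to the primary analysis.

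The size cannot be derived from the documents and is probably small: on GI, about 0.2 standard errors or less for two net withdrawals in one direction. That figure rests on assumed correlations, on an assumed number of withdrawals, and on the coordinator knowing enough about the product to select in one direction.

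**What to change.** In protocol 6.6, give the discretionary withdrawal decision to the blinded Principal Investigator in place of the investigator or the study coordinator. Let the coordinator raise a concern in writing without naming the product, and pause the rinse when safety is urgent until the investigator decides. Record on the withdrawal form who initiated it. Optionally, add to 6.6 that retaining and re-training under 5.1 is the default for noncompliance; nothing more is needed there.

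The cost is a short amendment, one form field and a site training note. There are no extra visits or examinations, and sample size, alpha and power do not change. A subject's own choice to leave and a severe reaction remain separate grounds in 6.6. The fix is partial: the coordinator keeps some influence through the concerns raised, and several other grounds in 6.6 still name no decision-maker.

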6.7 Blinding and Randomization

6.7.1 Blinding

The Principal Investigator and clinical examiners will be blinded to the treatment product assigned to study subjects. Efforts will be made to ensure that subject blinding is effective as

possible including precautionary measures such as subjects will be told not to open the non-transparent container containing study products until they return to their home and to bring all study supplies back to their next scheduled appointment in the same container. A subject blinding assessment will be completed after the first rinse dose and at the last study visit.

The blind will not be broken during the study unless 3M personnel decide to stop the study or it is necessary to break the blind for subject safety.

6.7.2 Randomization

A total of 200 subjects will be randomized to one of the four treatment groups in a 1:1:1:1 ratio. Random assignment will be provided in sealed envelopes that are to be opened in sequential order at the time the subject qualifies for the study.

7. STUDY PRODUCTS

7.1 3M Oral Rinse

The volume of 15 mL will be swished for 30 seconds followed by expectoration, twice a day (morning and evening), after brushing teeth, for the 6-month duration of the study as described in Appendix 17.1. Subjects will be instructed to use the dosing cup provided by the study team to ensure that the proper dose of rinse is used. They will be instructed not to use the product directly from the bottle (ie, put their mouth on the opening of the container) and to replace the cap after each use. Subjects will be instructed not to eat or drink for 30 minutes after using the rinse and to complete the subject daily diary.

7.2 Vehicle Control Oral Rinse Formulation

The volume of 15 mL will be swished for 30 seconds followed by expectoration, twice a day (morning and evening), after brushing teeth, for the 6-month duration of the study. Subjects will be instructed to use the dosing cup provided by the study team to ensure that the proper dose of rinse is used. They will be instructed not to use the product directly from the bottle (ie, put their mouth on the opening of the container). They will be instructed to replace the cap after each use. Subjects will be instructed not to eat or drink for 30 minutes after using the rinse and to complete the subject daily diary.

7.3 PerioShield Oral Health Rinse Predicate Device Control

PerioShield™ Oral Health Rinse (0.2% delmopinol hydrochloride) is marketed in the US and will be purchased for use in the study. The subjects will follow the product instruction for use using 10 mL for 30 seconds followed by expectoration, twice a day (morning and evening), after brushing teeth, for the 6-month duration of the study. Subjects will be instructed to use the dosing cup provided by the study team to ensure that the proper dose of rinse is used. They will

be instructed not to use the product directly from the bottle (ie, put their mouth on the opening of the container). Subjects will be instructed to replace the cap after each use. Subjects will be instructed not to eat or drink for 30 minutes after using the rinse and to complete the subject daily diary.

This rinse is a marketed product and will be over-labeled by 3M personnel in 3M's Manufacturing Technologies GMP facility, 3M Center, St. Paul, MN.

7.4 Water Control

The water control will be purchased sterile water and over-labeled by 3M personnel in 3M's Manufacturing Technologies GMP facility, 3M Center, St. Paul, MN.

Subjects will rinse with 15 mL for 30 seconds followed by expectoration, twice a day (morning and evening), after brushing teeth, for the 6-month duration of the study. Subjects will be instructed to use the dosing cup provided by the study team to ensure that the proper dose of rinse is used. They will be instructed not to use the product directly from the bottle (ie, put their mouth on the opening of the container). Subjects will be instructed to replace the cap after each use. Subjects will be instructed not to eat or drink for 30 minutes after using the rinse and to complete the subject daily diary.

7.5 Choice of Comparator

The comparators are two negative controls (water and vehicle oral rinse) and a positive control, PerioShield Oral Health Rinse, the predicate medical device.

7.6 Study Product Storage and Accountability

All test materials and study supplies will be provided by the study sponsor. All study products will be stored at the study site in a securely locked area only accessible to authorized personnel until dispensed to subjects.

Access to study products shall be controlled and shall be used only in the clinical study and per the study protocol. The sponsor shall keep records to document shipment of the study supplies to the study site as well as returned study supplies. The Principal Investigator or an authorized designee shall keep records documenting the receipt, use, return and disposal of the devices, which shall include:

- Date of receipt
- Identification of each study product
- Expiration date
- Date of distribution
- Subject identification

- Date on which the study product was returned, if applicable, and date of return of unused product

After completion of the study all unused study materials will be returned to 3M.

